9.1.2.2. Secondary efficacy endpoints

- i) Change in total amount of alcohol consumed per 4-week period after 6 months from "baseline." An ANOVA model for repeated measurements will be used to compare the groups.
- ii) Change in total amount of alcohol consumed per 4-week period after 12 months from "baseline." An ANOVA model for repeated measurements will be used to compare the groups.
- iii) Proportion of completely sober patients at 12 months A logistic regression model will be used to compare the groups.
- iv) Proportion of completely sober patients at 6 months. A logistic regression model will be used to compare the groups.
- v) Change from baseline in the number of heavy drink days per 4-week period at 6 and 12 months, respectively. An ANOVA model for repeated measurements will be used to compare the groups.
- vi) Change from "baseline" in the number of non-drinking days per 4-week period at 6 and 12 months, respectively. An ANOVA model for repeated measurements will be used to compare the groups. Förändring från "baseline" i antalet standardglas per dryckesdag per 4-veckorsperiod vid 6 och 12 månader, respektive. vii) Time to relapse (ie first alcohol intake). For

patients with the goal of becoming alcohol-free, relapse is defined as the first day after "baseline" where alcohol consumption was found, while relapse for patients with the goal of reducing alcohol consumption is defined as the first day after "baseline" where heavy alcohol consumption is found. Heavy consumption is defined for women as a day with 4 or more glasses, while for men it is defined as a day with 5 or more glasses. The data sources TripleA, TLFB or blood samples are used to detect recurrence. To compare the survival curves, ie. the variable time to recurrence, between the treatment groups a log-rank test will be used.

- vii) CGI improvement. The proportion of respondents at follow-up visits is compared between the groups with a logistic regression model.
- viii) EQ-5D. The groups are compared regarding change from "baseline" with ANOVA model. No significant difference is expected, as quality of life forms are generally not particularly sensitive to change after treatment.
- ix) Participation in treatment. To compare the survival curves, ie. the variable time until the treatment is stopped, between the treatment groups a log-rank test will be used.
- x) Compliance with TripleA. The proportion of measurements performed by those announced is calculated and reported for the TripleA arm.
- xi) Compliance with the agreed plan for visits to the care provider and / or visits to AA meetings. The treatment groups are compared with respect to the proportion of visits performed based on CRF data with a logistic regression model. For the TripleA arm, the corresponding data collected via TripleA and the correspondence between TripleA and CRF data are also evaluated.
- xii) Alcohol metabolites in the blood. Changes from baseline to 6 and 12 months, respectively, in PEth and CDT levels are calculated and the treatment groups are compared with an ANOVA model for repeated measurements.
- xiii) Evaluation of AUDIT data. The treatment arms will be compared with respect to:
 - xiv) - The proportion of patients who after 12 months have lowered their AUDIT score
 - xv) - The proportion of patients who after 12 months have lowered their AUDIT score to at least one zone
 - xvi) - Proportion of patients who after 12 months have a risk level <II (i.e. less than 6 AUDIT points for women, 8 AUDIT points for men).
- xvii) Evaluation of the number of "reds" and the number of missing blows in TripleA.

TripleA generates new types of high-resolution data that need to be handled in this and future clinical trials. In the simple case, the patient performs all agreed alcohol tests. For these, we can easily calculate the frequency of negative and positive alcohol tests in relation to a limit value for alcohol in the exhaled air. A fully sober patient has then probably performed 90 (3 / day) negative alcohol tests for 30 days in a month and can be considered 100% sober. A positive alcohol test ($> 0.1 \text{ mg / ml} = 0.2 \%$) gives a sobriety that is $1/90 = \sim 99\%$ or if it is calculated per day it will be 96.6% (29/30). What can be more complicated is to correlate this new type of high-resolution data with e.g. the number of days with large consumption from

patient-reported data in TLFB form. If there are 3 positive blows in one day, it is very likely also a heavy drinking day (≥ 4 standard glasses / day for women, ≥ 5 standard glasses / day for men), which is medically serious. If there are alcohol tests performed in the evening 3 different days with just over 0.2 %, it can correspond to 2 glasses of wine for dinner - which can be completely acceptable if the goal is to reduce drinking and its somatic and psychological consequences (risk reduction). If you detect around 0.2 % in the morning 3 different days, it can be serious and very well mean 3 heavy drinking days where the alcohol consumption took place after the last alcohol test in the evening and the body did not have time to burn all alcohol before the next test in the morning.

The second thing to deal with is missed alcohol tests. These may be due to the patient being sober but for various reasons not being able to perform the alcohol test in time (not noticed the notification, flight, mobile data shadow, etc.) or relapse into alcohol consumption. Here, the patient can contact the care provider (or vice versa) and clarify what happened.

The caregiver has the opportunity to enter a new classification for an individual test in the caregiver portal, which means that the database will contain supplementary information - without overwriting the basic status. The following options are available for missed tests:

- No alcohol
- Alcohol could not be excluded
- Technical issue.

If the default status is "Alcohol could not be excluded", the following status comments can be selected:

- No alcohol
- Technical issue.

If the basic status is "Technical error", the following status comments can be selected:

- No alcohol
- Alcohol could not be excluded

The patient also has an opportunity to show that they have not had a relapse by submitting blood samples for analysis of PEth and CDT. The caregiver can then reclassify the missed alcohol tests as above.

Even if the caregiver indicates a new classification on a test performed or missed, the original data always remains, which is so that the percentage sobriety can be calculated in two ways:

- o Proportion of sober tests based on all alcohol tests performed.
- o Corrected proportion of sober tests where both performed and missed alcohol tests are taken into account, with the classification made by the care provider as above.

9.1.3.Explorative analyses

We will initially summarize data from the TripleA alcohol tests as the proportion of sober days (both based on tests performed and corrected values (as above)) over a 4-week period immediately before a visit (1, 2, 3, 6.11 months). A positive alcohol test is > 0.10 mg / L alcohol in the breath test. The effect will be calculated against TLFB data transformed in a similar way. We will also perform correlation studies between TripleA and reported levels of PEth and CDT in blood samples.

The primary and secondary efficacy measures analyzed based on TLFB data will be compared with corresponding analyzes that also take into account blood test data and TripleA results.

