7.2.2. Secondary efficacy endpoints

Difference between the treatment arms in the proportion of completely sober patients during a 4-week period at 6 and 12 months, respectively.

The proportion of completely sober patients is measured with TLFB. To be considered sober, the patient must have entered 0 standard glasses consumed during the 4-week period preceding the 6- and 12-month visits, respectively.

The difference in the total amount of alcohol consumed per 4-week period after 6 and 12 months, respectively, compared with baseline

The total amount of alcohol consumed per 4-week period is measured in standard glasses using TLFB, and is the sum of the number of glasses for the entire period. How to determine the TLFB at baseline is stated in section 8.1.2. Follow-up TLFB is then made at each visit. The difference in the number of heavy drinking days per 4-week period at 6 and 12 months, respectively, compared with baseline

The number of heavy drinking days is measured with TLFB. Heavy drinking days are the same as days with heavy consumption, which means consumption of 4 or more standard glasses of alcohol per day for women and 5 or more standard glasses of alcohol per day for men. How to determine the TLFB at baseline is stated in section 8.1.2. Follow-up TLFB is then made at each visit.

The difference in the number of drink-free days per 4-week period at 6 and 12 months, respectively, compared with baseline.

The measuring tool becomes TLFB where the number of days of consumption specified as zero standard glass during a four-week period can be calculated. How to determine the TLFB at baseline is stated in section 8.1.2. Follow-up TLFB is then made at each visit..

The measuring tool becomes TLFB where the number of days of consumption specified as zero standard glass during a four-week period can be calculated. How to determine the TLFB at baseline is stated in section 8.1.2. Follow-up TLFB is then made at each visit.

The measuring tool becomes TLFB, where the sum of the number of standard glasses for the entire 4-week period is divided by the number of days when alcohol is consumed. How TLFB is to be determined at baseline is stated in section 8.1.2. Follow-up TLFB is then made at each visit.

Time to relapse

Depending on the goal of treatment, a relapse can be either a day of heavy consumption or drinking at least one standard glass of alcohol. Both recurrence measures will be evaluated.

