- The number of days before the first alcohol intake (at least one standard glass) according to the patient's own information.
- The number of days before the first heavy drinking day according to the patient's own information.

Clinical Global Impression improvements after 6 and 12 months, respectively

The patients who after 12 months are "significantly improved" or "greatly improved", ie they receive a value of 1 or 2 on the CGI-I scale (see section 8.3.6) are considered to have responded to the treatment (responders). Patients with a value of 3 or higher are classified as non-responders. The proportion of responders will be compared between the treatment arms.

Change in quality of life measured with EQ-5D

EQ-5D is an accepted and widely used measure of quality of life, and the form is recommended by TLV (Dental and Pharmaceutical Benefits Agency). A general quality of life measure such as EQ-5D provides an overall picture of the study participants' perceived health, and is a good basis for health economic analyzes.

AUDIT improvement

The National Board of Health and Welfare prioritises AUDIT as a tool for identifying alcohol problems. The treatment arms will be compared with respect to:

- Proportion of patients who after 12 months have lowered their AUDIT score
- Proportion of patients who after 12 months have lowered their AUDIT score to at least one zone
- Proportion of patients who after 12 months have a risk level <II
(i.e. less than 6 AUDIT points for women, 8 AUDIT points for men).

SADD improvement

Change in alcohol dependence measured as the difference in SADD scores at 12 and 6 months, respectively, compared with baseline).

Compliance with agreed treatment

The patient remains in treatment

At each study-related visit, it is documented whether the patient remains in treatment or has interrupted his or her treatment. The proportion of patients who remain in treatment will be compared between the patient groups over time.

Compliance with TripleA

For the TripleA arm, the proportion of measurements performed compared to announced measurements will be reported. The information is retrieved from the TripleA database where all notifications and measurements are logged. Corresponding information is not available for the control arm for obvious reasons.

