7.8.11. Factors that can affect the result

How motivated the patient is to abstain from alcohol will have an impact on whether one succeeds in abstaining from drinking alcohol during the course of the study. However, in order to make a study as realistic as possible, patients will not be selected depending on how motivated they are.

On the other hand, motivational factors will be mapped (see Appendix F) and thus you can get information on whether the degree of motivation in the two treatment groups is comparable or not, and whether it is possible to link the degree of motivation to the treatment result. The degree of severity of the dependence and the possible impact of demographic and social factors on the result will also be taken into account with exploratory analyzes.

The trust between therapist and patient can be of great importance for the treatment result and even if the methodology applied by the therapists is the same, it is conceivable that it matters which therapist you meet. Therefore, the randomization procedure will ensure that each therapist treats patients in both treatment arms to the greatest possible extent.

The treatment the patient receives may play a role in how the patient succeeds, but there is a lack of unambiguous data that suggests that a certain treatment works better than others, both in general and for specific patient groups. We therefore allow a wide range of treatment methods as background treatment in the clinical studies with TripleA. Descriptive statistics will be presented for what the distribution of treatment methods looks like in the various treatment arms. The patient material in the current study is probably too small to be able to draw any conclusions as to whether any treatment works better or worse in combination with TripleA, but exploratory subgroup analyzes will be performed.

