9.1. Statistical design, method and analysis procedure

9.1.1. General

Continuous data will be summarized using descriptive statistics where the following parameters will be reported: number of observations, number of missing observations, mean, standard deviation, median, minimum and maximum. Categorical data will be presented with number (n) and percentage (%).

In addition to evaluation of all study data from the entire study period (12 months), 6-month data will also be evaluated.

Factors such as gender, severity of addiction, motivation, form of therapy and socio-economic factors will be considered as covariates in the statistical analyzes.

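### The change-from-baseline ANOVAs for the continuous secondary endpoints do not name the outcome's own baseline value as a covariate, which gives away precision that could be had at almost no cost

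*Combined protocol and SAP*

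**What the plan says.** Section 7.2.2 defines several secondary endpoints relative to baseline, for example "The difference in the number of heavy drinking days per 4-week period at 6 and 12 months, respectively, compared with baseline". Section 9.1.2.2 turns these into models:

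- Total alcohol (items i and ii), heavy drinking days (item v: "Change from baseline in the number of heavy drink days per 4-week period at 6 and 12 months, respectively") and non-drinking days (item vi) go into a repeated-measures ANOVA.
- For the blood markers, "Changes from baseline to 6 and 12 months, respectively, in PEth and CDT levels are calculated", and the arms are again compared by repeated-measures ANOVA.
- Change in EQ-5D is compared by ANOVA.
- Section 7.2.2 also lists "Change in alcohol dependence measured as the difference in SADD scores at 12 and 6 months, respectively, compared with baseline", but section 9.1.2.2 gives no model for it.

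No model in section 9.1.2.2 names a covariate. The one general statement is in section 9.1.1: "Factors such as gender, severity of addiction, motivation, form of therapy and socio-economic factors will be considered as covariates in the statistical analyzes". The list is open-ended and is not tied to any endpoint. It does not mention the outcome's baseline value.

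The baseline values will exist. The study overview (7.3.14) and the visit 1 procedures (7.8.2) include TLFB, SADD, EQ-5D and blood samples, and section 7.8.2 places randomisation after them.

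**The concern.** Subtracting the baseline is not the same as adjusting for it. A change score fixes the coefficient on baseline at 1, whatever the data say. If baseline predicts follow-up only moderately, subtraction carries baseline noise into the outcome, and a chance difference between the arms at baseline is over-corrected. Putting the baseline value in the model lets the data set the coefficient.

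What is at stake is the width of the intervals on drinking quantity, heavy drinking days, abstinent days, PEth, CDT and EQ-5D. The trial is sized only for the binary primary endpoint, so precision on these outcomes is whatever the analysis can extract. Section 7.1.2 lets the TLFB baseline be a representative four weeks before the decision to seek help, and it is compared with drinking up to 12 months after visit 1. A modest correlation is therefore plausible, and that is where the loss is larger. This is an inference; the documents report no correlation.

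**Working it through.** **The plan's own figure.** Section 9.2 assumes 30% vs 60%, two-sided 5% and 80% power. With pooled variance, n per arm = [1.96·√(2·0.45·0.55) + 0.8416·√(0.3·0.7 + 0.6·0.4)]² / 0.3² = 3.777/0.09 = 41.97, so 42. With 20% loss, 42/0.8 = 52.5, so 53 per arm and 106 in total. The figure reproduces. It depends only on the binary primary endpoint, so nothing below alters it.

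**Does repeated-measures ANOVA already adjust?** Suppose baseline is one of the repeated time points. With complete data, the arm-by-time contrast at 12 months is (TripleA mean at 12 months − TripleA mean at baseline) − (control mean at 12 months − control mean at baseline). That is the difference in mean change. Adjustment would follow only if the baseline means were constrained to be equal across arms, which the plan does not state.

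**Variance at one follow-up visit.** Set the follow-up SD to 1, the baseline SD to k, and the baseline-to-follow-up correlation to r. The documents give neither k nor r, so both are assumed.

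- Unadjusted change score: 1 + k² − 2rk
- Follow-up (or change) with baseline as covariate: 1 − r²
- Difference: (1 + k² − 2rk) − (1 − r²) = (k − r)², which is never negative

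The ratio is therefore never below 1 and equals 1 only at k = r. With equal SDs (k = 1) it reduces to 2/(1 + r):

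| r | Change, 2(1 − r) | Adjusted, 1 − r² | Ratio | Interval wider by, √ratio − 1 |
|---|---|---|---|---|
| 0.2 | 1.60 | 0.96 | 1.67 | 29% |
| 0.3 | 1.40 | 0.91 | 1.54 | 24% |
| 0.5 | 1.00 | 0.75 | 1.33 | 15% |
| 0.7 | 0.60 | 0.51 | 1.18 | 8% |

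**Sensitivity to k**, same four correlations:

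- k = 0.75: 1.32, 1.22, 1.08, 1.00 (the last is 0.5125/0.51)
- k = 1.5: 2.76, 2.58, 2.33, 2.25

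**Reporting as change.** The model change = a + b·arm + c·baseline rearranges to follow-up = a + b·arm + (c + 1)·baseline. The arm effect b and its standard error are identical, so the endpoints can stay as section 7.2.2 defines them.

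**Patients lost.** None. Someone without a baseline value has no change score either, and the ITT population in section 9.2 already requires baseline efficacy data.

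**The case against.** The strongest reply is that this is a preference for a more efficient model, not an error. That stands. Under randomisation the change-score comparison is unbiased.

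The second reply concerns size. The table compares baseline adjustment with a change score that has no covariates, whereas section 9.1.1 says severity of addiction will be considered. This also stands. A severity term in the change model can only lower its residual variance, so the tabulated ratios are upper bounds for the equal-SD case. As an illustration, suppose severity correlates s with the outcome's baseline and relates to follow-up only through it (both assumed). The ratio becomes 1 + (1 − s²)(ratio − 1). At s = 0.5 and r = 0.2 this is 1 + 0.75 × 0.667 = 1.50, and the four values become 1.50, 1.40, 1.25 and 1.13. At s = 0.7 they are 1.34, 1.27, 1.17 and 1.09. Severity is not defined in section 9.1.1, however, and one severity measure cannot be the baseline of every outcome.

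Third, the primary analysis set is ITT with multiple imputation, so ratios for complete baseline and follow-up pairs are only a guide to the realised gain.

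Two stronger readings are tempting:

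- A reader might infer that the plan rules out baseline adjustment. It does not: the list in section 9.1.1 is open, so the term is unnamed rather than excluded.
- A reader might infer that sections 9.1.1 and 7.8.11 conflict, and that adjusting for form of therapy after randomisation would bias the comparison. Section 7.8.11 says "the possible impact of demographic and social factors on the result will also be taken into account with exploratory analyzes", and on background treatment "Descriptive statistics will be presented for what the distribution of treatment methods looks like in the various treatment arms" and "but exploratory subgroup analyzes will be performed". Considering factors as covariates and exploring them are compatible. Nothing says that therapy started after randomisation will enter an efficacy model.

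**Conclusion.** The point holds as an optional improvement. The change-from-baseline models for total alcohol, heavy drinking days, non-drinking days, PEth, CDT and EQ-5D omit a covariate that is already collected, and the repeated-measures structure does not supply it.

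Under equal SDs and correlations of 0.2 to 0.7, the variance penalty runs from 1.67 down to 1.18, as an upper bound if a severity covariate is also used. It is larger if baseline values are more spread out than follow-up values, and close to nil when k is near r. All of this rests on assumed r and k. For EQ-5D the plan expects no significant difference, so the gain there is simply a narrower interval.

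A reader might infer a biased test, or a threat to the main result. The documents support neither. The loss is one of precision on secondary endpoints; the logistic regression for the primary endpoint and the 106 patients are untouched.

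**What to change.** Add one rule to section 9.1.2.2: every analysis of change from baseline includes that outcome's own baseline value as a prespecified covariate.

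- In the repeated-measures models, include baseline and baseline-by-visit.
- For EQ-5D, use ANCOVA.
- Apply the rule to change in SADD as well, which currently has no stated model.
- Include the same baseline value in the multiple imputation model described in section 9.2, so that imputation and analysis agree.
- Continue to report results as change from baseline.

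The cost is one baseline parameter per follow-up visit modelled: two if only 6 and 12 months enter, and up to five if months 1, 2, 3, 6 and 12 all do. No new data are needed and the sample size stays at 106.
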